13.6.2. Study Population

Demographics
Age

 Age, in whole years, will be calculated with respect to the subject's Screening visit. GSK standard IDSL algorithms will be used for calculating age where birth date will be imputed as follows: 
 Any subject with a missing date and month will have this imputed as '30th June'. Birth date will be presented in listings as 'YYYY'. Completely missing dates of birth will remain as missing, with no imputation applied. Consequently, the age of the subject will not be calculated and will remain missing.
Body Mass Index

 Calculated as Weight (kg)/Height (m)²
Hepatitis Status

 Hepatitis C status will be determined using antibody and/or hepatitis C virus (HCV) RNA assessments performed during screening or during the conduct of the study. If both antibody and virus RNA assessments are available, then the latter will take precedence and positive/negative status will be based on whether HCV RNA is detectable (i.e., \geq limit of quantification) or not. A participant will be considered positive for hepatitis B virus (HBV) if they have a positive surface antigen or detectable HBV DNA result. "HBV DNA DETECTED" in the lab comment takes precedence over HBV DNA test result for positive hepatitis B status; for example, if a participant has HBV DNA test result below level of detection and the lab comment shows that HBV DNA detected, this participant will be considered positive for hepatitis B. If HBV DNA result is available, it will be used to qualify hepatitis B status as positive or negative (positive if \geq limit of quantification); otherwise Hepatitis B status will be determined using the surface antigen result. Hepatitis status at entry will be based on the assessments prior to/on the start of the study treatment.
Adherence to CAB/RPV Injection Schedule

 Timeliness of Injections relative to Date of Projected Dosing Visits are assessed by using "actual injection visit date - projected visit date from first injection". The injections of interest in adherence analysis are those after first injection at Month 1. (. Each injection visit is counted only once. Individual CAB and RPV injections administered at the same visit are not counted twice. "Extra" unscheduled injections are excluded from all derivations. For example, if during a scheduled visit a participant receives 1 ml of injection instead of 2 ml due to a dosing error, but this participant returns one week later for the remaining 1 ml injection, then the additional visit is excluded. If a participant receives an extra injection at an unscheduled visit by mistake, this visit will also be excluded. The categories of Timeliness of Injections relative to Date of Projected Dosing Visits are listed below: 
 < -14 days -14 to -8 days -7 to 1

Demographics	

 • 0 • 1 to 7 days • 8 to 14 days • >14 days • Missed Injection without Oral Bridging (COVID-19 related) • Missed Injection without Oral Bridging (Non COVID-19 related) • Missed Injection with Oral Bridging (COVID-19 related) • Missed Injection with Oral Bridging (non COVID-19 related) 	

 • Injection visits are expected monthly from Month 2 until the nominal month of a participant's last injection visit during the phase(s) of interest. For example: 
 • If a participant discontinues study treatment with last injection visit occurring at nominal visit Month 6 (without oral bridging), then injection visits are expected at Month 2, Month 3, Month 4, Month 5 and Month 6. • Missed injections occurring during periods of on-going oral bridging (e.g. oral bridging is ongoing at the time of the data analysis cutoff or participant discontinues study treatment where last study treatment received is oral bridging) are not considered to be expected visits. 	
Site Type	

 • AIDS Healthcare Foundation (Site Id.= PPD) • Federally Qualified Health Center (Site Id.= PPD) • Health Maintenance Organization (Site Id.= PPD) • Private Practice (Site Id.= PPD) • University (Site Id.= PPD) 	

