1.14.	Screened	SP1	Summary of Study Populations	GSK Statistical Display Standard	M12, EOS
1.15.	Enrolled	SP2	Summary of Exclusions from the Safety Population	GSK Statistical Display Standard	M12, EOS
Demographic and Baseline Characteristics					
1.16.	Safety	DM1	Summary of Demographic Characteristics	ICH E3, FDAAA, EudraCT. For EOS: add age group (18 - 24, 25 - 40, >40), BMI group (<30, >=30).	HL, M12, EOS
1.17.	Enrolled	DM11	Summary of Age Ranges	EudraCT	M12, EOS
1.18.	Safety	DM6	Summary of Race and Racial Combinations	ICH E3, FDA, FDAAA, EudraCT	M12, EOS
1.19.	Safety	BASELINE2	Distribution of CD4+ Cell Count Results at Screening and Baseline		M12, EOS*
1.20.	Safety	BASELINE3	Summary of Hepatitis Status at Entry		M12, EOS*
1.21.	Safety	CDC1	Summary of CDC Classification of HIV-1 Infection at Baseline		M12, EOS*

Study Population Tables					
No.	Population	GSK Standard / Example Shell	Title	Programming Notes	Deliverable
Prior and Concomitant Medications					
1.22.	Safety	MH1	Summary of Past Medical Conditions	ICH E3	M12, EOS*
1.23.	Safety	MH4	Summary of Past Cardiac, Gastrointestinal, Metabolism and Nutrition, Psychiatric, Renal and Urinary, Nervous System Conditions, and Hepatobiliary Disorders	ICH E3	M12, EOS*
1.24.	Safety	MH1	Summary of Current Medical Conditions	ICH E3	M12, EOS
1.25.	Safety	MH4	Summary of Current Cardiac, Gastrointestinal, Metabolism and Nutrition, Psychiatric, Renal and Urinary, Nervous System Conditions, and Hepatobiliary Disorders	ICH E3	M12, EOS
1.26.	Safety	CM9	Summary of Concomitant Medications by Ingredient Combinations	ICH E3 See GSK Statistical Display Standard Multi-ingredient medications will be labelled according to the sum of their ingredients, i.e., Generic Term.	M12, EOS
1.27.	Safety	207966/primary _15/T1.30	Summary of Prior Antiretroviral Therapy Medications	Remove the footnote. Follow definitions in Section 13.4.1 to determine the prior ART medications.	M12, EOS*

Study Population Tables					
No.	Population	GSK Standard / Example Shell	Title	Programming Notes	Deliverable
1.28.	Safety	201585/primary _02/T1.30	Summary of Antiretroviral Therapy Taken During Screening by Baseline Third Agent Class	Like Example shell but stratified by Baseline Third Agent Class (NNRTI,INI,PI); add 'Any' row under each class.	M12, EOS*
1.29.	Safety	RF1	Summary of HIV Risk Factors		M12, EOS*
Other					
1.30.	Safety	POP_T1	Summary of Transition to CAB + RPV LA Marketed Product Status by Site Type and Site ID		EOS

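### The two hepatitis B rules in SAP 13.6.2 give opposite answers for a surface-antigen-positive participant with HBV DNA below quantification and no laboratory comment that DNA was detected

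*SAP*

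**What the plan says.** Under Hepatitis Status, section 13.6.2 sets out the hepatitis B derivation in three steps.

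- **Either marker:** "A participant will be considered positive for hepatitis B virus (HBV) if they have a positive surface antigen or detectable HBV DNA result".
- **Laboratory comment:** a comment that HBV DNA was detected "in the lab comment takes precedence over HBV DNA test result for positive hepatitis B status". The SAP's example is a participant whose DNA result is below the level of detection but whose report carries the comment; that participant counts as positive.
- **DNA first:** "If HBV DNA result is available, it will be used to qualify hepatitis B status as positive or negative". Positive is then defined as a result at or above the "limit of quantification); otherwise Hepatitis B status will be determined using the surface antigen result".

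On timing, the section says: "Hepatitis status at entry will be based on the assessments prior to/on the start of the study treatment".

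The hepatitis C bullet just above orders its two tests explicitly: "If both antibody and virus RNA assessments are available, then the latter will take precedence".

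The derivation feeds Table 1.20, "Summary of Hepatitis Status at Entry", on the Safety population. It is delivered at Month 12, and again at end of study only if the underlying data have changed.

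**The concern.** The opening sentence treats a positive surface antigen as enough by itself. The later sentence ignores surface antigen whenever a DNA result exists. Nothing says that the later sentence replaces the opening one. The author did state precedence where it was meant, both for hepatitis C and for the laboratory comment.

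Two programmers working faithfully from this section could produce different hepatitis B counts for the same data. Table 1.20 is the display dedicated to this derived status, and Appendix 13 plans no participant-level hepatitis listing in which a discordant pair of results would show. At stake is whether the baseline description of the study population is reproducible.

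**Working it through.** The SAP gives no figure to reproduce, so the check is to apply both rules to every possible input.

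**Inputs, all from section 13.6.2**
- Surface antigen: positive, negative or missing.
- HBV DNA: at or above LOQ, below LOQ, or missing.
- Laboratory comment that DNA was detected: present or absent.

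That is 3 × 3 × 2 = 18 combinations. Three pair a comment with a missing DNA result and are not feasible, leaving 18 − 3 = 15.

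**Reading of the rules**
- Either-marker rule: positive if antigen is positive, DNA is detectable or the comment is present; otherwise negative if at least one marker is available. Detectable is read as at or above LOQ, as the hepatitis C bullet defines it.
- DNA-first rule: positive if the comment is present; otherwise DNA decides if available (positive at or above LOQ); otherwise antigen decides.

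**Results**

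| Antigen | DNA | Comment | Either-marker | DNA-first |
|---|---|---|---|---|
| any of 3 | at or above LOQ | yes or no | positive | positive |
| any of 3 | below LOQ | yes | positive | positive |
| **positive** | **below LOQ** | **no** | **positive** | **negative** |
| negative | below LOQ | no | negative | negative |
| missing | below LOQ | no | negative | negative |
| positive | missing | no | positive | positive |
| negative | missing | no | negative | negative |
| missing | missing | no | missing | missing |

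The rows cover 6 + 3 + 1 + 1 + 1 + 1 + 1 + 1 = 15 combinations. Fourteen agree and one conflicts. A looser reading of detectable could not remove the conflict, because antigen alone satisfies the either-marker rule.

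**Direction.** In the conflicting row the DNA-first rule turns a positive into a negative. No row goes the other way, so it can only lower the count.

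**Scale.** The SAP gives no prevalence and no number of participants with both tests. With the planned N of 115 (section 2.3), one such participant is 1/115 = 0.9 percentage points. Assuming between none and three, purely for illustration, the difference between the two rules runs from 0 to 3/115 = 2.6 points.

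**The case against.** The best defence is that the text contains one algorithm. The opening sentence says which markers count, and the later one gives the operative order: DNA if available, otherwise antigen. This runs from general to specific and mirrors hepatitis C, where nucleic acid comes before serology. On that reading every combination has a single answer. But the opening sentence is then untrue for the disputed case, and an antigen-positive entrant is reported as negative. The comment rule does not help either, because the conflict arises only when the comment is absent. The wording still needs correcting.

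The objections to the size of the problem stand.

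- **Liver safety results.** A reader might infer that they are compromised. The only listed subgroup is site type (section 5.4.2). The liver tables (3.34 to 3.36) and the hepatic AESI table (3.48) are not specified by hepatitis status, so only an informal reading against Table 1.20 is affected.
- **A count biased towards zero.** A reader might infer this on the ground that prior antiretroviral therapy suppresses HBV DNA. The SAP does not say so. It supports the direction of the difference, not its size.
- **Table 1.20 as the only window on hepatitis B at entry.** This is not established. Tables 1.24 and 1.25 report current conditions, including hepatobiliary disorders. Listing 5 would show the case if hepatitis B is an eligibility criterion.
- **Frequency.** Eligibility sits in the protocol, which was not available. If it excludes antigen-positive people, the disputed case holds only eligibility deviations.

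**Conclusion.** The contradiction is real and confined to one of 15 combinations. In that case the participant's status, and hence the HBV-positive count in Table 1.20, depends on which sentence is programmed. The number affected cannot be determined from the SAP and may be zero; the 0 to 2.6 point range rests on an assumed none to three participants out of 115. No hypothesis is tested (section 2.4), the primary analysis concerns implementation endpoints in a separate plan (section 7), and no endpoint or subgroup analysis uses hepatitis status. This is a small derivation error worth correcting, with no bearing on the trial's main conclusions.

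**What to change.** Replace the two conflicting sentences with one rule that is consistent with the opening sentence and the comment rule, using assessments on or before treatment start:

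- **Positive** if surface antigen is positive, or HBV DNA is at or above LOQ, or the laboratory comment says HBV DNA was detected.
- **Negative** if none of these holds and at least one of surface antigen or HBV DNA is available.
- **Missing** if neither is available.

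Delete the wording that lets a DNA result below LOQ override a positive surface antigen. Applied to the 15 combinations, this classifies the disputed one as positive and leaves the other 14 unchanged, including antigen missing with DNA below LOQ, which stays negative. Optionally, show surface antigen and DNA results separately in Table 1.20, so that discordant pairs are visible.

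The cost is a short wording change and a one-line change to the derivation. The HBV-positive count may come out slightly higher than under the DNA-first rule.

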2.2. Study Objective(s) and Estimand(s) / Endpoint(s)

Objectives	Estimands / Endpoints
Primary	Primary

 To evaluate acceptability, appropriateness, and feasibility of delivering CAB+RPV LA 	
 Acceptability of Intervention Measure (AIM), Intervention Appropriateness Measure (IAM), and Feasibility of Intervention Measure (FIM). Assessed quantitatively by staff study participants at baseline- prior to any Month 1 visits, after at least 4 monthly facilitation calls and upon completion of all Month 12 visits at that site. Acceptability of Intervention Measure (AIM) and Intervention Appropriateness Measure (IAM). Assessed quantitatively by patient study participants at Month 1 prior to first injection, Month 4 and Month 12
Secondary	Secondary

 To evaluate organizational facilitators and barriers 	
 Facilitators/Barriers: Semi-Structured Interview (SSI) conducted with staff study participants at baseline- prior to any Month 1 visits, after at least 4 monthly facilitation calls and upon completion of at least 50% of Month 12 visits at that site. Barriers, facilitators and best practice sharing amongst clinics assessed by short-term facilitation (coaching calls) for at least 6 months. These will be a combination of structured questions and open-ended questions. Use of support materials/toolkit assessed via Survey responses of staff study participants prior to any Month 1 visits, after at least 4 monthly facilitation calls and upon completion of all Month 12 visits at a site. Use of support materials/toolkit assessed via Survey responses of patient study participants via Survey responses at Month 1 and Month 4 and Month 12, as well as SSI responses prior to Month 1 and at Month 12.

 Patient Facilitators and Barriers 	
 Facilitators/Barriers: Semi-Structured Interviews (SSI) conducted with patient study participants prior to Month 1 and at Month 12.

Objectives	Estimands / Endpoints

 Implementation Fidelity 	
 Injections occurring within target window from the expected injection date Use of support materials/toolkit assessed through SSI of staff study participants at Day 1, after at least 4 monthly facilitation calls and upon completion of at least 50% of Month 12 visits at that site

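### Expected injections are counted only up to the last injection received, so final missed injections leave the adherence denominator and on-time proportions can only be biased upward

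*SAP*

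**What the plan says.** SAP 13.6.2 (Adherence to CAB/RPV Injection Schedule) sorts injections after Month 1 by how far they fall from the projected date. It adds four categories for missed injections, split by oral bridging and by relation to COVID-19; one is "Missed Injection without Oral Bridging (Non COVID-19 related").

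The denominator rule is: "Injection visits are expected monthly from Month 2 until the nominal month of a participant's last injection visit during the phase(s) of interest". The SAP illustrates it with a participant who leaves, as follows: "If a participant discontinues study treatment with last injection visit occurring at nominal visit Month 6 (without oral bridging), then injection visits are expected"; the months it then lists are 2, 3, 4, 5 and 6.

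A second rule removes "Missed injections occurring during periods of on-going oral bridging". It covers bridging that is ongoing at the data cut-off and bridging that is the last treatment before discontinuation.

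The derivation feeds Tables 3.3 and 3.4 (Intervention Phase; Month 12 headline and Month 12 analysis) and Tables 3.5 and 3.6 (end of study). They are presented by visit and by site type or site ID, and are this plan's only summaries of injection timing. SAP 2.2 lists under Implementation Fidelity: "Injections occurring within target window from the expected injection date".

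**The concern.** Whether a visit is expected depends on whether an injection was given then or later in the phase. That is the behaviour the tables are meant to describe, so the outcome sets its own denominator. The same non-attendance is a missed injection if the participant comes back within the phase, and disappears if the participant does not.

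This is an implementation study, and the tables compare sites and site types. The misses that disappear are those at the end of a participant's injections, including those that lead up to discontinuation. A site with such misses would show a more favourable adherence figure than its attendance supports.

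**Working it through.** **Inputs**

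- Denominator rule, example and missed categories: SAP 13.6.2.
- N = 115 and at most 15 patients per site: SAP 2.3.
- Intervention Phase injections stop before Month 13: SAP 13.6.4, Extent of Exposure.
- Tables 3.5 and 3.6 name no phase in their titles, so they cover Intervention plus Extension: opening note of SAP 13.13.
- Discontinuation and missed-injection rates: not in the plan, so assumed in step 5.
- The table shells are not shown. I take on-time injections divided by expected visits as the proportion of interest.

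**Step 1: the plan's own example.** If L is the nominal month of the last injection, expected visits = L − 1. L = 6 gives 5, which reproduces Months 2, 3, 4, 5 and 6. L = 1 gives 0, so someone injected only at Month 1 contributes nothing.

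**Step 2: final misses.** Months 2 to 6 are on time; the participant then misses t projected injections before discontinuation is recorded. Plan: 5/5. Counted: 5/(5 + t).

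| t | Plan | Counted |
|---|---|---|
| 0 | 100% | 100% |
| 1 | 100% | 83.3% |
| 2 | 100% | 71.4% |
| 3 | 100% | 62.5% |

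A final miss adds to the denominator and never to the numerator. For any number k of final misses, a/(b + k) ≤ a/b, so the bias has one direction.

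**Step 3: earlier misses.** Month 4 missed, last injection at Month 6: 4/5 = 80%. The plan counts this miss.

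**Step 4: Month 12.** Anyone who misses Month 12 has a last Intervention Phase injection at Month 11 or before, so Month 12 is not expected. The missed rows at Month 12 in Tables 3.3 and 3.4 are zero by construction. A participant on time for Months 2 to 11, who misses Month 12 and is injected at Month 13, has L = 11 and is shown as 10/10 instead of 10/11 = 90.9%. In Tables 3.5 and 3.6, L is at least 13, so the same miss is counted. The two sets of tables then disagree about one participant-visit.

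**Step 5: pooled size under assumptions.** D of 115 participants leave, each with a last injection at Month 6; the others have 11 expected visits (Months 2 to 12). Of the visits the plan counts, 95% are on time. Denominator b = 11(115 − D) + 5D; corrected proportion = 0.95b/(b + Dt).

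| Leavers | b | t = 1 | t = 2 | t = 3 |
|---|---|---|---|---|
| 5% (D = 6) | 1229 | 94.5% | 94.1% | 93.6% |
| 10% (D = 12) | 1193 | 94.1% | 93.1% | 92.2% |
| 20% (D = 23) | 1127 | 93.1% | 91.3% | 89.5% |

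Against the plan's 95.0%, the overstatement runs from 0.46 points (D = 6, t = 1) to 5.48 points (D = 23, t = 3). With 90% on time the range is 0.44 to 5.19 points.

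**Step 6: one site, one visit.** With 15 patients, 14 injected on time and one final miss, the plan gives 14/14 = 100% instead of 14/15 = 93.3%.

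**The case against.** Several stronger readings are tempting, and the SAP does not support them.

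- A reader might infer that every injection missed before a participant leaves is lost. Step 3 shows otherwise: a miss followed by a later injection in the same phase is expected and has its own category.
- A reader might infer that the last expected visit is always a success. It is an injection given, but it may fall in any of the early or late categories.
- A reader might infer that the Implementation Fidelity endpoint is shown to be overstated. SAP 2.2 is not expressly tied to Tables 3.3 to 3.6, and SAP section 7 sends implementation-science analyses to a separate plan. Overstatement also needs at least one final miss.
- A reader might call the bridging exclusion an error. It is a stated choice, and SAP 13.6.1 includes oral bridging in study treatment. Showing those visits separately is a better answer than reclassifying them.

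It can also be said that these tables measure timeliness, and that retention is reported elsewhere: disposition and withdrawal in Tables 1.1 to 1.4, reasons for stopping treatment in Listing 2, COVID-19 deviations by site in Table 1.12. That stands in part. Those displays show who left and why, but the SAP does not say that any of them counts non-COVID-19 injections missed between the last injection and discontinuation. Table 1.13 covers implementation deviations by site without saying that these misses are included.

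The best practical objection concerns the remedy. If counting runs to the recorded discontinuation date, a site that pursues patients longer before recording withdrawal accumulates more misses. This is a real limitation and argues for showing final misses in their own row. It does not remove the one-directional bias, and it does not touch the Month 12 case, which needs no dropout.

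**Conclusion.** The concern holds in this limited form. Injections missed after the last one received in the phase of interest, and before discontinuation, end of phase or data cut-off, are absent from both the expected and the missed counts. The on-time proportion in Tables 3.3 to 3.6 can therefore be too high but not too low on this account. The absence of missed injections at Month 12 in Tables 3.3 and 3.4, and the possible conflict with Tables 3.5 and 3.6, follow from the rule itself and rest on no assumed rate.

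The pooled size cannot be computed from the plan. About 0.5 to 5.5 points is a range under the assumptions of step 5, and it is zero if nobody has a final miss. Leaving out visits after treatment discontinuation is reasonable and is not part of the point. The study is descriptive, with no hypothesis test, so what is at stake is the reported adherence and the comparison of sites. The definition should be changed.

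**What to change.** In SAP 13.6.2, count projected injection visits from Month 2 up to the earliest of the recorded permanent treatment discontinuation date, the end of the phase of interest and the data cut-off. Class any such visit without an injection as missed. State whether a projected visit whose window is still open on that date counts.

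Show two groups in rows of their own: final misses before discontinuation, and misses during ongoing or final oral bridging. The figure under the present rule then stays visible beside the fuller one. A footnote should say that the final-miss count depends on when discontinuation was recorded.

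The cost is one change of wording and one derivation; SAP 13.4.1 (Table 8) already uses the discontinuation date. Adherence will look slightly less favourable, and the new count will vary with how promptly sites record discontinuation. The change concerns the analysis definition only and leaves dosing untouched.
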